#### **8.9.4 Analysis Limitations**

The results of this study can be generalizable only to patients included in the HIRA population which is the entire Korean population. Results should not be generalized to other patient populations or healthcare systems outside Korea.

#### **8.9.5 Missing and/or Incomplete Data**

This study does not account for unobserved confounders. No information is provided in the database as to why patients may discontinue treatment. Further, no information is available regarding medications the patients may have received as over-the-counter treatment or as samples from the physician, as well as medications paid for out of pocket.

### **8.10 Other aspects**

Not applicable.

## **9. PROTECTION OF HUMAN SUBJECTS**

### **9.1. Patient Information and Consent**

Informed consent is not required for this study, because this study is secondary data collection study using fully anonymized data.

### **9.2. Patient withdrawal**

Not Applicable.

### **9.3. Institutional Review Board (IRB)/Independent Ethics Committee (IEC)**

It is the responsibility of the investigator to have prospective approval of the study protocol, protocol amendments, and informed consent forms, and other relevant documents, (e.g., recruitment advertisements), if applicable, from the IRB/IEC. All correspondence with the IRB/IEC should be retained in the Investigator File. Copies of IRB/IEC approvals should be forwarded to Pfizer.

### **9.4. Ethical Conduct of the Study**

The study will be conducted in accordance with legal and regulatory requirements, as well as with scientific purpose, value and rigor and follow generally accepted research practices described in Guidelines for Good Pharmacoepidemiology Practices (GPP) issued by the International Society for Pharmacoepidemiology (ISPE), Good Epidemiological Practice (GEP) guidelines issued by the International Epidemiological Association (IEA), Good Practices for Outcomes Research issued by the International Society for Pharmacoeconomics and Outcomes Research (ISPOR), International Ethical Guidelines for Epidemiological Research issued by the Council for International Organizations of Medical Sciences (CIOMS), management and REPORTING of adverse events/adverse reactions

This study includes unstructured data (e.g., narrative fields in the database) that will be converted to structured (i.e., coded) data solely by a computer using automated/algorithmic

methods and/or data that already exist as structured data in an electronic database. In these data sources, it is not possible to link (i.e., identify a potential association between) a particular product and medical event for any individual. Thus, the minimum criteria for reporting an adverse event (AE) (i.e., identifiable patient, identifiable reporter, a suspect product, and event) are not available and AEs are not reportable as individual AE reports.

## 10. PLANS FOR DISSEMINATING AND COMMUNICATING STUDY RESULTS

The results of this research will be submitted for publication in a peer-reviewed journal and will be submitted for presentation in either poster or oral format at a medical or outcomes based research conference.

Authorship of any publications resulting from this study will be determined on the basis of the International Committee of Medical Journal Editors (ICJME) Recommendations for the Conduct, Reporting, Editing and Publication of Scholarly Work in Medical Journals, which states:

- Authorship credit should be based on (1) substantial contributions to conception and design, acquisition of data, or analysis and interpretation of data; (2) drafting the article or revising it critically for important intellectual content; (3) final approval of the version to be published and (4) agreement to be accountable for all aspects of the work in ensuring that questions related to the accuracy or integrity of any part of the work are appropriately investigated and resolved. Authors should meet conditions 1, 2, 3 and 4.

All publications (eg, manuscripts, abstracts, oral/slide presentations, book chapters) based on this study must be submitted to Pfizer for corporate review. The vendor agreement will detail the procedures for, and timing of, Pfizer's review of publications.

## COMMUNICATION OF ISSUES

In the event of any prohibition or restriction imposed (e.g., clinical hold) by an applicable Competent Authority in any area of the world, or if the investigator is aware of any new information which might influence the evaluation of the benefits and risks of a Pfizer product, Pfizer should be informed immediately.

In addition, the investigator will inform Pfizer immediately of any urgent safety measures taken by the investigator to protect the study patients against any immediate hazard, and of any serious breaches of this NI study protocol that the investigator becomes aware of.

## 3. ANNEX 1. LIST OF STAND ALONE DOCUMENTS

None.

## 4. ANNEX 2. ENCEPP CHECKLIST FOR STUDY PROTOCOLS

Not applicable.

## **5. ANNEX 3. ADDITIONAL INFORMATION**

Not applicable.

1 AMENDMENTS FROM PREVIOUS VERSION(S)

Amendment number	Date	Substantial or administrative amendment	SAP section(s) changed	Summary of amendment(s)	Reason
Amendment 01 (V2.0)	31Jan2018	Substantial amendment	2.1 STUDY DESIGN	Add “Comparative analyses will be performed contingent on a feasibility assessment based on the descriptive analyses.” Clarify the reference period for AF diagnosis	Meet to Harmonized SAP
		Substantial amendment	2.2 STUDY OBJECTIVES	Change phrases aligned with protocol	According to protocol amendment
		Substantial amendment	3 ANALYSIS SETS/ POPULATIONS	Change Inclusion & Exclusion criteria	According to protocol amendment
		Substantial amendment	4.1 EFFICACY/ EFFECTIVENESS ENDPOINT(S)	Add ‘Hemorrhagic stroke’ in operational definition	Meet to Harmonized SAP
		Substantial amendment	4.2 SAFETY ENDPOINTS	Change to ‘Major bleeding’ Delete the ‘Clinically relevant non-major bleeding’	Meet to Harmonized SAP
		Substantial amendment	5.1 STATISTICAL METHODS	Add Balance diagnostics & IPTW diagnostics	Specify the analysis method for propensity score
Amendment 02 (V3.0)	23Apr2018	Substantial amendment	2.Study design	Add ‘other NOACs, new use of warfarin, and aspirin’ Delete ‘ aspirin-clopidogrel combination, and clopidogrel’	More detailed description of the objectives
		Substantial amendment	2.2 study objectives	Delete ‘to explore baseline characteristics and drug utilization patterns of antithrombotic therapies in special patients groups (i.e., coronary intervention patients)	This secondary objective will have a separate protocol (in agreement with global HEOR team guidance)
		Administrative amendment	3.1 diagnosis codes for inclusion criteria	Add ‘ [NOTE] KCD code is based on ICD-10 and almost similar, but KCD code is slightly different from ICD-10 (e.g., ICD-10 is more subdivided and extensive than KCD code	More details on the difference between ICD-10 and KCD codes provided
		Administrative amendment	3. 1 Exclusion criteria	Delete ‘ hip or knee replacement’ in medical claims indicating a diagnosis code of others during the 12-month baseline period	Conflicts with the exclusion criteria #1;duplicate
		Administrative amendment	3. 1 Exclusion criteria	Revise #6 as ‘for the comparison of “NOAC versus NOAC”, and “NOAC versus warfarin, patients with any OACs (apixaban, dabigatran, rivaroxaban, or warfarin)	More clear statements for NOAC vs NOAC and NOAC vs VKA comparison

NIS Protocol <X9001134>
 Statistical Analysis Plan
 <Version 3.0> <03 May 2018>

Amendment number	Date	Substantial or administrative amendment	SAP section(s) changed	Summary of amendment(s)	Reason
				in the pre-index period	
		Substantial amendment	3.1 Exclusion criteria	Revise #7 as 'for the comparison of "NOAC versus aspirin", patients with following medications in the pre-index period (from 1 year prior to the day before index date)	More clear statements for NOAC vs aspirin
		Administrative amendment	3.1 Cohorts	Add statements on dataset for NOAC vs NOAC, NOAC vs warfarin, NOAC vs aspirin	Details provided for each comparison cohorts
		Administrative amendment	3.1 Cohorts	Delete ' [Note] clopidogrel, aspirin, clopidogrel will be included in descriptive analysis'	Deleted the statement for relocation
		Administrative amendment	3.2 Subgroups	Revise as 'subgroup analysis may be considered, including but not limited to subgroup analyses by...'	More broad statements to cover various topics for sub-analyses
		Substantial amendment	4.1 Efficacy/effectiveness endpoints	Revise to include hospitalization and CT/MRI imaging for all outcomes, more explanation on how the events were measured Add 'individual outcome of primary outcome' Deleted myocardial infarction	Corrected errors
		Substantial amendment	4.2 Safety endpoints	Add statement regarding main subdiagnosis codes being used Add ' hospitalization and brain CT/MRI to identify ICH' Add individual outcome of major bleeding, clinical events preceding each pattern, compliance	More clear statements added
		Administrative amendment	5.1 Descriptive analysis	Add ' the proportion of antithrombotics at index date will be examined'	More details on the treatment pattern provided
		Administrative amendment	5.1 Multivariate analysis	Specific comparison cohorts for analysis Add statements on covariate adjustment propensity score Delete references used under IPTW diagnostics Add statements for each comparison cohorts	More clear statements included
			5.1 Statistical methods	Additional sensitivity analysis	Perform IPTW using the propensity score derived from multinomial model
		Substantial amendment	5.2 Statistical analyses	Add ' other propensity score method will also be used'	More clear statements included

NIS Protocol <X9001134>
Statistical Analysis Plan
<Version 3.0> <03 May 2018>

Amendment number	Date	Substantial or administrative amendment	SAP section(s) changed	Summary of amendment(s)	Reason
		Administrative amendment	6. Summary of analyses	Delete 'myocardial infarction'	Removed for accuracy
		Administrative amendment	8. Appendix	Add statements regarding bleeding outcomes and procedures codes	More details provided
		Substantial amendment	Appendix 2. Data derivation details	Revise codes for effectiveness and safety outcomes codes	Input codes according to changes in the outcome endpoints
		Substantial amendment	Table 13. Exclusion criteria	Add codes for each conditions	More details provided
		Substantial amendment	Table 14. Blood transfusion codes	Add codes for Korean procedure codes used	More details provided

2 INTRODUCTION

Atrial fibrillation (AF) is the most common persistent arrhythmia, and its prevalence has been estimated to be 1-2% of the general population, with a progressive increase (1). AF increases the risk of ischemic stroke by five-fold and is associated with 15% of stroke for all age groups and 30% in patients aged 80 years and older (2). Patients with AF-related ischemic stroke have higher recurrent risk, morbidity, and mortality as compared to patients with other types of stroke (3). Thus, current clinical guidelines for AF emphasize stroke prevention in patients with AF, in the presence of stroke risk factors (4). Effective stroke prevention essentially requires oral anticoagulants (OAC) therapy. Vitamin K antagonists (i.e., warfarin) effectively decrease the risk for thromboembolic events in patients with AF (5). However, vitamin K antagonists have several limitations, including need for regular blood monitoring and possibility for food or drug interactions. This had led to the quest for new OACs that would be more safe and effective than warfarin (6). In randomized controlled trials, NOACs demonstrated noninferior or superior reduction in stroke and systemic embolism when compared to warfarin (7-10).

Physicians now have a choice between the available NOACs but have relatively little evidence to guide their decision-making because of no head-to-head trials of these drugs. In addition, there have been far fewer studies on efficacy and safety outcomes of NOACs. The nationwide claims database in Korea can provide an opportunity to study comparative effectiveness and safety outcomes of NOACs in patients with atrial fibrillation in Korea.

2.1 STUDY DESIGN

This study will use a retrospective cohort design in which the treatment effectiveness and safety outcomes of new use of NOACs compared to other NOACs, new use of warfarin, and aspirin will be estimated in patients with atrial fibrillation using the Korean Health Insurance Review & Assessment Service (HIRA) database. Comparative analyses will be performed contingent on a feasibility assessment based on the descriptive analyses. Propensity score method and Cox proportional hazards models will be used to account for selection bias, differences in follow-up time, and right data censoring. This will allow us to minimize selection bias and confounding bias and provide outcome data amenable to rapid clinical interpretation (i.e., time-to-event analysis, hazard ratios). Furthermore, HIRA database will allow us to preserve the population-based longitudinal data collection advantages. The overall study design is described in Figure 1.

[figure not shown]

Figure 1. Study design scheme

Study population

Subjects with atrial fibrillation (between January 1, 2007 up to and including the index date*) who newly initiated NOACs, warfarin, or used aspirin between July 1, 2015 and November 30, 2016 in the Korean Health Insurance Review & Assessment Service (HIRA) database.

*Index date is the first prescription date of study drugs, including NOACs, warfarin, and aspirin.

Data source

South Korea has a universal health coverage system that the National Health Insurance covers approximately 97% of the overall South Korean population. The claims data of Health Insurance Review & Assessment Service (HIRA) contains 46 million patients per year that account for 90% of the total population in Korea and include claims from almost 80,000 healthcare service providers across South Korea as of 2011.

The claims data of HIRA includes patients' diagnosis, treatment, procedures, surgical history, and prescription drugs which provide a valuable resource for healthcare service research. Data elements captured in the HIRA database include patient-level demographic and plan enrollment information (e.g., start and stop dates of health plan enrollment), date-stamped (month and year) inpatient and outpatient medical claims (e.g., diagnosis codes, procedure codes, provider specialty), and pharmacy claims (e.g., prescription fill/refill dates, drug name/code, dosage). While procedure codes that identify patient receipt of laboratory tests are available, actual laboratory values and test results are not available.

The HIRA database has unique attributes that make it a useful data source for this study. The key advantage of the HIRA database relative to other potential data sources (e.g., medical chart review) is that it is a population level data including most of Korean population and it will provide a large analytic sample and provide accurate claim-level treatments pattern and health care utilization across all provider settings (e.g., inpatient, outpatient, pharmacy) in patients' spectrum of care.

One key limitation of the HIRA database is that it does not include clinical variables such as laboratory values and clinical markers. To overcome this limitation, the Charlson comorbidity index and overall healthcare utilization observed during the pre-index period will be used as proxy measures to incorporate the overall health status of the individual patients.

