#### ***Secondary objectives***

1. To explore and understand more detailed drug utilization patterns
  - o Standard doses versus reduced doses of NOACs

- Patterns of usage (i.e., switching, discontinuation) and clinical events preceding the pattern
- Compliance (i.e., medication possession ratio)

2. To compare effectiveness and safety of antithrombotic therapies versus not using therapies among low risk patients (low score of CHA2DS2-VASc)

**Study design:** Retrospective cohort study

**Population:** Subjects with atrial fibrillation diagnosed (from January 1, 2007 up to and including the index date\*) who newly initiated antithrombotic therapies (NOACs (not including edoxaban), warfarin, or used aspirin) between July 1, 2015 and November 30, 2016 in the Korean Health Insurance Review & Assessment Service (HIRA) database

*\*Index date is the first prescription date of study drugs, including NOACs, warfarin, and aspirin during the intake period (from July 1, 2015 to November 30, 2016).*

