### 8.2.2 Exclusion criteria

Patients meeting any of the following criteria will not be included in the study.

1. Medical claims indicating diagnosis or procedure for hip/knee replacement surgery within 6 weeks prior to index date
2. Medical claims indicating a diagnosis code indicative of rheumatic mitral valvular heart disease, mitral valve stenosis during the 12-month baseline period  
(Valvular AF / Prosthetic heart valves)
3. Medical claims indicating a diagnosis code of VTE (Venous thromboembolism) during the 12-month baseline period
4. Medical claims indicating a diagnosis or procedure code of transient AF, or cardiac surgery during the 12-month baseline period

(Thyrotoxicosis, Hypertrophic cardiomyopathy, Elective defibrillation, radiofrequency ablation, or left atrial appendage occlusion)

5. Medical claims indicating a diagnosis code of other conditions during the 12-month baseline period  
(End-stage chronic kidney disease / Kidney transplant / Dialysis / Pericarditis)
6. For the comparison of “NOAC versus NOAC”, and “NOAC versus warfarin”, patients with any OACs (apixaban, dabigatran, rivaroxaban, or warfarin) in the pre-index period (from 1 year prior to the day before index date)
  - *[NOTE] Patients prescribed antiplatelets in the pre-index period will not be excluded.*
7. For the comparison of “NOAC versus aspirin”, patients with following medications in the pre-index period (from 1 year prior to the day before index date)
  - NOAC user: OACs (apixaban, dabigatran, rivaroxaban, warfarin)
  - Aspirin user: none
  - *[NOTE] NOAC user is defined as OAC naïve user and aspirin user is allowed to have OACs or antiplatelets in the pre-index period.*

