## 8.6 Data management

### Obtaining data files

Pusan National University team will submit the data request form to HIRA. After the HIRA committee review, the data will be uploaded in the server. The study team will access the data through the remote access using IP address. All medical or pharmacy claims and demographic information from January 1, 2007 to November 30, 2016 of patients with atrial fibrillation (KCD code: I48) from July 1, 2015 to November 30, 2016 will be accessed.

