6. For the comparison of “NOAC versus NOAC”, and “NOAC versus warfarin”, patients with any OACs (apixaban, dabigatran, rivaroxaban, or warfarin) in the pre-index period (from 1 year prior to the day before index date)
 - *[NOTE] Patients prescribed antiplatelets in the pre-index period will not be excluded.*
7. For the comparison of “NOAC versus aspirin”, patients with following medications in the pre-index period (from 1 year prior to the day before index date)
 - NOAC user: OACs (apixaban, dabigatran, rivaroxaban, warfarin)
 - Aspirin user: none
 - *[NOTE] NOAC user is defined as OAC naïve user and aspirin user is allowed to have OACs or antiplatelets in the pre-index period.*

Cohorts

To avoid increasing type I error when multiple comparisons occur, this full analysis set will be splitted into multiple sub-analysis sets as follows:

1. NOAC vs NOAC (both as OAC naïve users)
 - A. Sub-dataset 1: patients with index treatment of apixaban and patients with index treatment of dabigatran
 - B. Sub-dataset 2: patients with index treatment of apixaban and patients with index treatment of rivaroxaban
 - C. Sub-dataset 3: patients with index treatment of dabigatran and patients with index treatment of rivaroxaban

[NOTE] The index date will be defined as date of the first prescription of NOAC in patients with NVAF. To identify new users, a look-back observation period from 1 year prior to the day before the index date will be used and must indicate no OAC use during this period. The diagnosis date of NVAF could occur from January 1, 2007 up to and including the index date.

2. NOAC vs warfarin (both as OAC naïve users)
 - A. Sub-dataset 4: patients with index treatment of apixaban and patients with index treatment of warfarin
 - B. Sub-dataset 5: patients with index treatment of dabigatran and patients with index treatment of warfarin
 - C. Sub-dataset 6: patients with index treatment of rivaroxaban and patients with index treatment of warfarin

[NOTE] The index date will be defined as date of the first prescription of NOAC or warfarin in patients with NVAF. To identify new users, a look-back observation period from 1 year prior to the day before the index date will be used and must indicate no OAC use during this period. The diagnosis date of NVAF could occur from January 1, 2007 up to and including the index date.

3. NOAC (OAC naïve user) vs aspirin (no restrictions of antiplatelet or OAC use in the pre-index period)

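### OAC-naïve status is tested over one year only, although pharmacy claims since 2007 are held and earlier OAC use is not currently a named covariate or the subject of a sensitivity analysis

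*SAP*

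**What the plan says.** SAP 2.1 frames the study as a comparison of "new use of NOACs compared to other NOACs, new use of warfarin, and aspirin will be estimated in patients with atrial fibrillation". The operative rule is in SAP 3.1: to identify new users, "a look-back observation period from 1 year prior to the day before the index date will be used", and it "must indicate no OAC use during this period". Protocol 8.2.2, criterion 6, says the same for NOAC versus NOAC and NOAC versus warfarin, by excluding "patients with any OACs (apixaban, dabigatran, rivaroxaban, or warfarin) in the pre-index period (from 1 year prior to the day before index date"). The cohort headings in SAP 3.1 then label the patients who pass, for example "NOAC vs warfarin (both as OAC naïve users"). The NOAC arm of sub-datasets 7-9 carries the same label through criterion 7. The aspirin arm does not, because earlier OAC use is openly allowed there.

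The intake period runs from 1 July 2015 to 30 November 2016. The footnote on the population in the protocol abstract reads "Index date is the first prescription date of study drugs, including NOACs, warfarin, and aspirin during the intake period". Protocol 8.6 states what will be accessed: "All medical or pharmacy claims and demographic information from January 1, 2007 to November 30, 2016 of patients with atrial fibrillation". SAP 3.1 lets the AF diagnosis fall anywhere from 1 January 2007 to the index date.

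Past OAC use is absent from Protocol 8.3, SAP Table 4, the medication classes of SAP Table 12 and the table shell for baseline characteristics, although antiplatelet history is in all of them. SAP 5.1 gives examples of propensity covariates (age, sex, the three scores, comorbidities) and leaves the final list until after the descriptive results. Its only sensitivity analysis is IPTW with a multinomial propensity score. Protocol 8.9 does not list the short look-back as a limitation.

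**The concern.** The plan uses nearly a decade of claims to establish AF but only one year to establish that a patient is new to anticoagulants. Someone with AF since 2008 who took warfarin for some years, stopped, and restarts in 2016 is analysed beside someone who has never had an OAC.

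This matters if two things are true together: former users differ in outcome risk from first-time starters after adjustment, and they are spread unevenly over the arms. The documents make uneven spread plausible for NOAC versus warfarin. SAP Table 3 names stroke, embolism and major bleeding as events after which physicians might change anticoagulant, and the SAP introduction names practical drawbacks of warfarin. Either could steer a former warfarin user towards a NOAC, while one who did well on warfarin might return to it. Nothing in the documents suggests a comparable sorting between apixaban, dabigatran and rivaroxaban, so the argument is weaker for sub-datasets 1-3.

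At stake are the stroke and bleeding hazard ratios of sub-datasets 4-6 and the description of those cohorts as naïve.

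**Working it through.** **Look-back held and used**
- Claims start on 1 January 2007 (Protocol 8.6).
- Earliest index, 1 July 2015: 8.5 years of history. The rule searches 1 year, or 1/8.5 = 11.8%, and leaves 7.5 years unsearched.
- Latest index, 30 November 2016: 9.9 years of history. The rule searches 1/9.91 = 10.1% and leaves 8.9 years unsearched.

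**Who is affected**
Only former users whose last OAC claim was more than one year before index. Anyone with a more recent claim is excluded. Former NOAC users are affected as well as former warfarin users.

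**Size**
The plan states no figure to reproduce: the expected 150,000 patients is a head count from disease statistics, and the share of former users is not given. The inputs below are therefore assumptions.

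Let pA and pB be the shares of former users in the two arms, and RR their outcome rate relative to first-time starters, left over after adjustment. The average rate in an arm is proportional to 1 + p(RR − 1), so the true hazard ratio is multiplied by approximately

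factor = [1 + pA(RR − 1)] / [1 + pB(RR − 1)].

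With pA = 15% and pB = 5%:

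| RR | Calculation | Factor |
|---|---|---|
| 0.5 | 0.925 / 0.975 | 0.95 |
| 0.8 | 0.970 / 0.990 | 0.98 |
| 1.0 | 1 / 1 | 1.00 |
| 1.2 | 1.030 / 1.010 | 1.02 |
| 1.5 | 1.075 / 1.025 | 1.05 |
| 2.0 | 1.150 / 1.050 | 1.10 |

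Other shares, for RR 0.5 and RR 2.0:
- 10% v 5%: 0.950/0.975 = 0.97 and 1.100/1.050 = 1.05.
- 20% v 5%: 0.900/0.975 = 0.92 and 1.200/1.050 = 1.14.
- Imbalance reversed, 5% v 15%: 0.975/0.925 = 1.05 and 1.050/1.150 = 0.91.
- Equal shares: 1.00 at any RR.

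**Whether the plan already covers it**
The multinomial IPTW changes the form of the propensity model, but no text adds past OAC use to it. Charlson and healthcare utilisation are offered as proxies for health status, and SAP 2.1 says utilisation is observed in the pre-index period, which the exclusion criteria set at one year. HAS-BLED counts bleeding history and stroke, but no look-back is stated for it, so an event that ended warfarin years earlier may or may not be captured. SAP Table 4 says that labile INR is not available.

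**The case against.** The one-year washout is stated openly and identically in both documents, and the naïve label stands beside the rule that defines it. This objection stands: a reader might infer that the documents contradict themselves or misstate the cohort, but they do not. The label is broader than the test behind it, and more exact wording would cure that.

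The propensity list is given by example and is to be settled later, and the protocol abstract says its key covariates are not exhaustive. So it would be wrong to infer that adjustment for past OAC use has been ruled out. It is simply not named. The open list is only partial protection, because the descriptive tables meant to inform the final choice do not include the variable.

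The bleeding pathway may be partly adjusted for through HAS-BLED, and prior stroke through both risk scores. That also stands, with the unstated look-back as the limit. It is why RR above must be read as a residual rate ratio, which could be close to 1.

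A reader might infer a known bias, for instance against NOACs. The documents give no prevalence, no imbalance and no outcome rate for former users, so no direction can be claimed.

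Finally, the SAP index-date notes for sub-datasets 1-6 speak of the first prescription without repeating the intake period. Read as first ever, they would remove former users of the same drugs. The protocol abstract limits the index to the intake period, and for NOAC versus warfarin a first-ever reading would make the one-year look-back redundant.

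**Conclusion.** The point holds as an avoidable weakness in confounding control, not as an error or inconsistency. Former OAC users with a gap of more than one year enter the NOAC and warfarin arms as naïve starters. The data to identify them are held, and the plan does not commit to using them. The concern is clearest for sub-datasets 4-6 and less clear for 1-3.

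Under assumed shares of 15% v 5% and a residual rate ratio of 0.5 to 2.0, the hazard ratio is multiplied by about 0.95 to 1.10. The effect is nil if the shares are equal or the residual rate ratio is 1, and it changes direction if the imbalance reverses. It may prove negligible, but the plan as written would not show that. A distortion of this kind does not shrink as the sample grows. The change should be made, although the main analysis can otherwise stand.

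**What to change.** 1. Keep the one-year washout as the entry rule.
2. Add to SAP Table 4 and the propensity models a flag for any OAC claim from 1 January 2007 to one year before index, and report it by arm in the baseline table.
3. Add a sensitivity analysis, at least for sub-datasets 4-6, restricted to patients with no OAC claim since 2007.
4. Describe the main cohorts as having no OAC claim in the prior year.

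The cost is one derived variable and one restricted re-run on data already held. There are three downsides to state. The restricted run has fewer patients and wider intervals. The look-back varies from 8.5 to 9.9 years with the index date. And Protocol 8.9.3 says continuous enrolment cannot be ensured, so the absence of a claim does not prove that a patient never took an OAC.
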